10.2. Analysis Set

10.2.1. Intended-to-treat Set (ITT)

Defined as all subjects who are enrolled in the randomized trial. The ITT population will be the main analysis population for the efficacy analysis of this study. Subjects will be analyzed based on the treatment group they are assigned.

10.2.2. Per Protocol Set (PPS)

PPS is a subset of the ITT. Refers to all randomized subjects who have received the protocol-specified single-dose treatment without significant protocol deviations that significantly affect the main efficacy. PPS-based analysis will complement ITT-based analysis as a supporting analysis. Subjects will be analyzed based on the treatment arm they plan to assign.

10.2.3. Safety Data Set (SS)

SS is defined as all subjects who received at least one test drug. The safety analysis population is the main analysis population for safety data. Subjects will be analyzed based on their actual assigned treatment arm.

10.3. Analysis methods

10.3.1. General principles

The statistical analysis uses SAS9.2 (or above) version of statistical analysis software, and the analysis process is all programmed. For continuous variables, the descriptive statistics will include the mean, median, standard deviation, maximal and minimal values (mean and median will be accurate to one more digit decimal point than the original data, and standard deviation will be accurate to two more digit decimal points than the original data, and the decimal points of

the maximum and minimum values will be the same as the original data, usually up to four decimal points are kept in the statistics table). Qualitative or grade indicators are summarized using descriptive statistics including the number of subjects, percentages, and / or number of events. The detailed statistical analysis plan and method will be described in detail in the statistical analysis plan.

10.3.2. Distribution of subjects

Descriptive statistics will be used to summarize the number of subjects screened, the number of screening failures, enrollment, entry into each analysis set (and reasons for excluding each analysis set), termination of treatment, withdrawal from the study, and follow-up. The number and percentage of subjects who entered each analysis set, discontinued treatment and study will be summarized by treatment arms.

10.3.3. Demographics, Medical History, and Baseline Characteristics

Demographic information and baseline characteristics, case history, and concomitant medications for all randomized subjects will be summarized using descriptive statistical methods based on randomization.

10.4. Efficacy Analysis

10.4.1. Primary efficacy endpoint

The primary endpoint “Time to Clinical Improvement” (TTCI) will be the time (days) from the randomization in which the patient's clinical status improved from baseline (scale 2-4, NIAID ordinal scale, [Appendix A](#)) to 5 or above that is sustained without a drop to below 5 within 28 days. Hospital discharge date (NIAID scale 7 or 8) is an important event time point. The date that clinical status evaluation ≥ 5 or the date of hospital discharge, whichever comes first will be used as the TTCI date.

The record of re-hospitalization with oxygen therapy is required to modify the TTCI date. The new TTCI date should be the time from randomization to the latest clinical status evaluation ≥ 5 or the date of the latest hospital discharge, whichever comes first.

Time to clinical improvement (days) is calculated as:

Time to Improvement = Date of (First Clinical Improvement/hospital discharge) – Date of Randomization

The discharge to home due to clinical improvement is scored as NIAID scale ≥ 7 . The date that clinical status evaluation ≥ 5 or the date of hospital discharge, whichever comes first will be used as the clinical improvement date. All subjects without clinical improvement within 28 days will be censored on the Day 29 visit.

The Log-Rank Test will be used to compare the following two sets of curves to test the following hypotheses:

$H_0: St(t) = Sp(t)$ vs. $H_1: St(t) > Sp(t)$ for improvement;

St(t) represents the improvement probability function of the experimental group, and Sp(t) represents the improvement probability function of the control group.

The probability function of clinical improvement will be estimated by Kaplan-Meier method. The median time and its 95% confidence interval for each group will be reported. The 95% confidence interval for the median time will be estimated using the Brookmeyer-Crowley method with log-log function conversion to achieve a normal approximation. The improvement rate will be estimated by the layered Cox-Model. Cumulative improvement rates estimated by the KM method for days 4, 8 and 15 and/or 29 their 95% confidence intervals will also be reported.

Time-event efficacy endpoints / censorship rules

For the primary endpoint, during the observation period, an improvement from NIAID scale 2, 3 or 4 to scale 5 or above, if sustained without a drop below 5, is considered as an event. The days from the randomization to the first time point of such improvement will be defined as time of improvement. Additional follow-up can be used to determine clinical improvement events.

Subjects who do not withdraw or do not experience improvement will be censored on the actual date of the D29 visit.

Subjects without improvement but lost to follow-up will be censored on the last date of follow-up.

Subjects with death within 28 days will be censored on D29.

Sensitivity analysis:

(1) Imbalances in age, baseline score, use of antiviral drugs such as remdesivir, or IL-6/IL-6R antagonist, or related factors that may affect the results will be investigated with sensitivity analyses and these factors will be evaluated separately in the Cox-Model to assess their potential impact on the primary efficacy endpoint.

(2) Use only data from planned visits to analyze time to improvement in the main analysis.

(3) The days from randomization to the first clinical improvement will be analyzed.

Since there are no available best supportive case (BSC) for this disease, controlling BSC use between two arms is difficult, and consequently there may be imbalance for some particular BSCs between two arms. To evaluate whether there may be some potential bias caused by such imbalance, we will evaluate the percentage of the largest and second largest BSC used in the trial if the difference of such BSC between two arms are significant. Further analyses will be performed to study whether the efficacy results are indeed caused by such differential BSC use between two arms.

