Time to improvement in clinical status: the time (days) to the improvement of clinical status from “scale 2 to 4” to “scale 5 or above that is sustained without a drop to below 5” based on NIAID 8-point ordinal scales ([Appendix A](#)) within 28 days from randomization.

Secondary Endpoints:

- Proportion of patients who died or had respiratory failure, defined as the need for mechanical ventilation, ECMO, non-invasive ventilation, or high flow oxygen devices, at Day 29;
- Time to disease progression in clinical status: the time (days) for progression from scale 3 or 4 to scale 1 or 2, or 2 to 1, based on NIAID ordinal scale with 28 days from randomization;
- All-cause mortality at Day 15 and Day 29;
- Proportion of clinical relapse, as defined by rate of return to oxygen support for more than 1 day within 28 days from randomization after initial recovery;
- Conversion rate of clinical status on days 8 (proportion of subjects who changed from “scale 2 to 4” to “scale 5 or higher” on NIAID ordinal scale);
- Conversion rate of clinical status on days 15 (proportion of subjects who changed from “scale 2 to 4” to “scale 5 or higher” on NIAID ordinal scale);
- The discharge time
- Duration of mechanical ventilation (IMV, NIV) (days);
- Duration of pressors;
- Duration of extracorporeal membrane oxygenation (days);
- Duration of oxygen therapy (oxygen inhalation by nasal cannula or mask) (days);
- Length of hospital stay (days);
- Absolute lymphocyte count;
- D-dimer concentration in the plasma.

Exploratory endpoints:

- Effect of CD24Fc on systemic steroid usage;
- Effect of CD24Fc on cytokine levels;
- Effect of CD24Fc on lymphocyte subtype distribution.

Safety evaluation:

- Adverse events, vital signs, laboratory tests (blood routine, blood biochemistry, coagulation function, urine routine), ECG.

Study Population:

Hospitalized severe and critical COVID-19 adult patients.

Eligibility Criteria:

Inclusion criteria

- 1) Should be at least 18 years of age.

- 2) Male or female, female should have negative pregnancy test.
- 3) Diagnosed with COVID-19 and confirmed SARS-CoV-2 viral infection, prior positive viral results allowed.
- 4) Informed consent form signed by the patient or by the legally authorized representative.
- 5) Hospitalized and requiring oxygen support, NIAID 8-point ordinal score 2, 3 or 4, regardless of ARDS ([Appendix A](#)). The intubation for mechanical ventilation is within 7 days.

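### Section 10.4.1 gives two conflicting rules for dating the primary event and does not say which governs

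*Combined protocol and SAP*

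**What the plan says.** **Rule 1, the sustained rule.** The Synopsis defines the endpoint as time to "scale 5 or above that is sustained without a drop to below 5" within 28 days of randomization. Section 2.4 and the opening sentence of 10.4.1 carry the same condition. Under the censoring rules in 10.4.1, an improvement from 2, 3 or 4 to 5 or above, "if sustained without a drop below 5, is considered as an event". Its date follows: "The days from the randomization to the first time point of such improvement will be defined as time of improvement".

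**Rule 2, the dating sentences earlier in 10.4.1.** The default date is the earlier of an evaluation at 5 or more and hospital discharge, with no condition that the improvement lasts. The formula starts from "Date of (First Clinical Improvement/hospital discharge". For a change of date, "The record of re-hospitalization with oxygen therapy is required to modify the TTCI date". The new date then runs to the "latest clinical status evaluation ≥ 5 or the date of the latest hospital discharge, whichever comes first". Discharge counts as improvement because "The discharge to home due to clinical improvement is scored as NIAID scale" 7 or above.

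Sensitivity analysis (3) in the same section reads: "The days from randomization to the first clinical improvement will be analyzed".

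**The concern.** Rule 2 does not carry the sustained condition of Rule 1, and no sentence gives either rule precedence. They agree for a patient who never relapses. They can differ for a patient who reaches 5, goes back onto oxygen and recovers again. The plan foresees such patients: clinical relapse is a secondary endpoint, and 10.4.2 describes it as starting from score 5 while still in hospital.

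For any patient without a re-hospitalization, the formula in Rule 2 also makes the primary date the same as the date in sensitivity analysis (3), which is evidently meant to differ from it.

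At stake is the only primary endpoint. Two programmers working from the same text could derive different event dates for the same patient, and the choice could end up being made after the data are seen.

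**Working it through.** **Step 1: apply both rules to the same patients.** All courses are illustrative.

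| Patient | Rule 1 | Rule 2, read literally | Reading that removes the difference |
|---|---|---|---|
| (a) Off oxygen Day 6, on again Day 9, off from Day 15, one stay | Day 15 | No re-hospitalization, so Day 6 stays: 15 − 6 = 9 days early | The record requirement covers only changes after discharge, and Rule 1 governs |
| (b) Discharged Day 6, readmitted on oxygen Day 12, off oxygen from Day 20, still an inpatient | Day 20 | min(evaluation on Day 20 or later, discharge Day 6) = Day 6: 14 days early | Latest discharge means discharge from the readmission (none yet), and latest evaluation means the latest change to 5 or more |
| (c) As (b), discharged again Day 23 | Day 20 | If latest evaluation means the last record: min(Day 23 or later, Day 23) = Day 23, 3 days late | Latest evaluation means the latest change to 5 or more: min(20, 23) = 20 |
| (d) Off oxygen Day 5, discharged Day 7, readmitted on oxygen Day 12, dies Day 20 | No event | Event at Day 7 | The definition sets event status |
| (e) Off oxygen Day 5, on again Day 7 in the same stay, dies Day 20 | No event | Event at Day 5 | The definition sets event status |

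A readmitted patient who goes straight from oxygen to a second discharge gets the same date under both rules.

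**Step 2: how many patients.** The plan gives no figure to reproduce here and no relapse rate, so the relapse rates are assumptions. Section 10.1 gives a control median of 11 days, HR 1.54 (drug median 7.14 days), exponential times and 135 per arm. Expected first improvers by Day 28:

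- control: 135 × (1 − 2^(−28/11)) = 135 × 0.829 = 111.9
- drug: 135 × (1 − 2^(−28/7.14)) = 135 × 0.934 = 126.1
- total: 238

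At 5%, 10% and 15% relapse, that is about 12, 24 and 36 relapsers.

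**Step 3: effect on the test.** The simulation used 10,000 trials per scenario, with improvement times rounded up to days, non-events held to Day 29 and a log-rank test at one-sided 0.025. Further assumptions:

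- Half of relapsers recover 4–10 days later, and this is an event if it falls by Day 28.
- 25, 50 or 75% of relapsers are of type (a)/(b) and keep the first date if they recover.
- The other recovered relapsers are type (c), dated at a discharge 1–5 days after coming off oxygen (Rule 1 date kept if that falls after Day 28).
- Relapsers who never recover are non-events under both rules, so only dates differ.

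The HR is applied to first improvement, so power under Rule 1 need not equal the 80% in Section 10.1. Results for the 25/50/75% splits:

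| Scenario | Power, Rule 1 | Power, Rule 2 dates | Rules disagree on significance |
|---|---|---|---|
| HR 1.54, relapse 10%/10% | 0.815/0.810/0.812 | 0.814/0.808/0.814 | 0.014/0.021/0.023 |
| HR 1.54, 5%/5% | – | – | 0.009/0.011/0.012 |
| HR 1.54, 15%/15% | – | – | 0.020/0.025/0.025 |
| HR 1.35, drug 10%, control 5% | 0.329/0.324/0.325 | 0.326/0.336/0.350 | 0.017/0.022/0.033 |
| HR 1.35, drug 5%, control 10% | 0.734/0.733/0.726 | 0.733/0.725/0.709 | 0.013/0.021/0.026 |

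The gap between the last two rows comes from relapse removing events, not from the dating rule. With no effect and equal relapse of 5–15%, the one-sided rejection rate is 0.023–0.028 under each rule.

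At HR 1.54 and 10% relapse, 2.7/5.4/8.1 patients are dated too early and 7.6/5.1/2.5 too late, about 10–11 in all. Scaled to 5–15% relapse, this is about 5–16 of 270. These counts apply the literal reading to every recovered relapser except those whose second discharge falls after Day 28, so they sit at the high end.

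**The case against.** The best defence is that the section, read as a whole, already gives the right answer.

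- Rule 1 stands under the heading for events and censoring and dates the event correctly.
- Sensitivity analysis (3) would be redundant if the primary analysis used plain first improvement.
- The re-hospitalization sentence can be read as an evidence rule for changes after discharge. Under Appendix A a discharged survivor scores 7 or 8 even on home oxygen, so only readmission or death can produce a later drop.
- The text speaks of modifying the date and of a new date. That suggests the discharge that counts is the one from the readmission.
- In the default sentence, an evaluation at 5 or more sensibly means the day the score reaches that level.
- Section 10.3.1 leaves detail to a statistical analysis plan.

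Much of this stands. A reader might infer that patient (b) is misdated on any reading, or that the plan has no sustained dating rule. Neither is supported: the readings in the last column of the table are available, and Rule 1 is in the text.

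A reader might also infer that relapsers who never recover will count as events. If Rule 2 did set event status, power at HR 1.54 and 10%/10% relapse would be 0.842/0.864/0.895 and the rules would disagree in 5.8–11.0% of trials. But the definition, the censoring rules (which hold deaths to D29) and sensitivity analysis (3) all point to no event for these patients, so that figure does not describe the plan as intended.

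What the defence does not remove is that nothing in the text selects these readings. Patient (a) needs one reading of the record requirement, (b) needs two readings together, and (c) needs one.

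**Conclusion.** The point holds as a conflict between two dating rules for the sole primary endpoint, with no stated precedence. It does not hold as a certain misdating. The expected effect is small: with equal assumed relapse of 5–15% and event status set by the definition, power and type I error are essentially unchanged and the conclusion changes in about 1–2.5% of trials.

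A reader might infer a bias in favour of the drug. The documents do not support that, because they give no relapse rate by arm. In the unequal-relapse scenarios, with most relapsers of type (a)/(b), Rule 2 dates raised power when the drug arm relapsed more and lowered it when the control arm did.

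The size rests on assumed relapse rates, recovery fraction, timing and mix of cases. The textual conflict rests on none of these. It is worth correcting because one rule should fix the primary event date in advance.

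**What to change.** Before unblinding, state one algorithm in 10.4.1 or in the statistical analysis plan to which 10.3.1 refers. The sample size re-estimation at 146 events in 10.5 needs the same dates.

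- Time to improvement is the first day of the final unbroken run of scores of 5 or more, with discharge counted as 7 or more, lasting to Day 28 or the last available assessment.
- Any in-hospital score below 5, any re-hospitalization at score 2–4, or death breaks the run.
- If there is no such run, there is no event, and the existing censoring rules apply.
- Delete *First* from the formula, and delete the sentence that takes the earlier of the latest evaluation and the latest discharge.
- Keep the re-hospitalization record only as the data source for drops after discharge.
- Keep time to first improvement as sensitivity analysis (3) only.

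The cost is wording and programming. No new data are needed: inpatient scores are recorded daily (7.1.12), status after discharge is captured at study visits (Table 2, footnote 5), and readmission records show any drop between visits.

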7.1.12. Evaluation of clinical status

Clinical status should be evaluated and recorded daily when the patient is hospitalized. The screening period must assess the clinical status and recorded as baseline.

If the patient clinical status improves and is discharged to home care, the follow up visits should follow the study schedule ([Table 2](#)), and the visits can be carried out through telemedicine (phone or video interviews). The clinical investigators should make best effort to obtain the vital signs, clinical status evaluation, concomitant medicines and adverse events assessment. The laboratory tests, radiology study, ECG and research samples are optional.

7.2. **REQUIRED OBSERVATIONS (STUDY CALENDAR as in Synopsis)**

7.2.1. **Screening period**

Visit 1

- Sign the informed consent by patient or by a legally authorized representative;
- Record the past medical history;
- Collect demographic data;
- Record vital signs and physical examination;
- Laboratory tests should be done according to Section 7.1.5. Tests done 72 hrs prior to screening are allowed;
- Record digital oxygen saturation;
- Arterial blood gas analysis (optional, tests done 72 hrs prior to screening are allowed);
- Pregnancy check (women only, under 54 years old);
- ECG. Tests done 72 hrs prior to screening are allowed;
- Chest CT scan or X-ray. Tests done 72 hrs prior to screening are allowed;
- Detection of SARS-CoV-2 viral nucleic acids. Prior positive viral results are allowed;
- Clinical status assessment;
- Collect blood samples for serum cytokines and lymphocyte subtypes (selected sites only);
- Confirm the inclusion / exclusion criteria;
- Record concomitant medications.

7.2.2. **Treatment / follow-up observation period (D1 ~ D29)**

Visit 2 (D1)

- Record vital signs before study drug infusion and at 60±10 minutes after the start of drug infusion;
- Confirm the inclusion / exclusion criteria;
- Subject is randomized;
- Chest CT examination (optional);
- Record digital oxygen saturation;
- Arterial blood gas analysis (optional);

- Laboratory tests according to Section 7.1.5;
- ECG before drug infusion, and at 2 hrs (120 ± 15 min) after drug infusion;
- Study drug administration;
- Clinical status assessment;
- Record IMV / NIV, ECMO, or oxygen therapy;
- Collect blood samples for serum cytokines and lymphocyte subtypes (selected sites only);
- Record adverse events and concomitant medications.

Visit 3 (D4 \pm 2d)

- Record vital signs;
- Clinical status assessment;

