10. STATISTICAL ANALYSIS

10.1. Sample size

In the phase III trial, the patients will be randomized at 1: 1 ratio into CD24Fc or placebo arms. It was assumed that the time to improvement the clinical status of the patients obeyed the exponential distribution, and the improvement hazard ratio (HR) was 1.54. The median time to improvement in the control group is presumed 11 days, and the median time to improvement in the treatment group is projected as 7.14 days. An interim analysis for efficacy will be performed when 70% of the required events are reached. The O'Brien-Fleming type consumption function of the Lan-DeMets algorithm is used to control the overall class I error rate $\alpha = 0.025$ (one-sided), at least 80% of the degree of confidence. At least 208 events are required to achieve 80% power. Assuming 28 days of patient follow up, the estimated number of 208 events will be reached for the final analysis approximately 28 days after the last subject is enrolled. Assuming 78% recovery rate, 270 participants will be enrolled in this trial.

The sample size was calculated on SAS 9.4 PROC SEQDESIGN.

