10.4.2. Secondary efficacy endpoints

Proportion of death or respiratory failure, defined as the need for mechanical ventilation, ECMO, non-invasive ventilation, or high flow oxygen devices at D29. Cumulative number of subjects reaching the composite endpoint vs number of people in the ITT population. Chi-square test will be used to compare the difference between the two arms.

For the disease progression, during the observation period, a progression from scale 3 or 4 to scale 2 or 1, or from 2 to 1, is considered as an event. The days from the randomization to the first time point of progression will be defined as time of progression. The probability function of clinical progression will be estimated by Kaplan-Meier method. The median time and its 95% confidence interval for each group will be reported. The 95% confidence interval for the median time will be estimated using the Brookmeyer-Crowley method with log-log function conversion to achieve a normal approximation. The progression rate will be estimated by the layered Cox-Model. Cumulative progression rates estimated by the KM method for day 29 and the 95% confidence intervals will be reported.

All-cause mortality at Day 15 and Day 29: the Mantel-Haenszel stratum-weighted estimator of the risk difference will be used to compare the treatments.

Rate of clinical relapse, defined as proportion of patients who have initially reached score 5 (hospitalized, without oxygen therapy) for more than one day but subsequently become dependent on oxygen support. Since responders are not based on the randomization, a descriptive statistic will be reported and an exploratory analysis using a Chi-square test will be performed.

Improvement rate of clinical status on Days 8 and 15 (proportion of subjects with clinical improvement): percentage of subjects with clinical improvement on Day 8 or 15 in the ITT population. Chi-square test will be used to compare the difference between the two arms.

The discharge time starts from randomization to discharge. T-tests will be used to compare the differences between the two groups in completers.

Duration of each major treatment (days): Descriptive statistics will be analyzed for mechanical ventilation (IMV, NIV), extracorporeal membrane oxygenation, duration of oxygen therapy, and length of hospital stay.

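### The primary log-rank test states no strata although the baseline NIAID score is recorded. Stratifying by that score, and naming it in the layered Cox and mortality analyses, is a cheap gain in power if it predicts recovery and the hazard ratio is similar across scores.

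*Combined protocol and SAP*

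**What the plan says.** Section 10.4.1 specifies the primary test: "The Log-Rank Test will be used to compare the following two sets of curves to test the following hypotheses". The hypotheses compare one improvement function per arm, and no strata are stated. The effect estimate is described separately: "The improvement rate will be estimated by the layered Cox-Model". No layers are named.

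Section 10.4.2 does the same for progression ("The progression rate will be estimated by the layered Cox-Model"). For all-cause mortality, "the Mantel-Haenszel stratum-weighted estimator of the risk difference will be used to compare the treatments", again without strata. Section 11.9.1 describes a computer-generated randomization list and names no stratification factor, so no strata can be carried over from the randomization.

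Section 4.1 admits patients at NIAID score 2, 3 or 4, from invasive ventilation or ECMO to supplemental oxygen. Section 7.1.12 says "The screening period must assess the clinical status and recorded as baseline". Sensitivity analysis (1) in section 10.4.1 lists baseline score among factors that may affect the results, to be examined one at a time in a Cox model. Section 10.3.1 leaves detail to a statistical analysis plan, and the available text contains no strata from it.

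**The concern.** There are two linked points.

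**Undefined strata.** The two Cox models and the mortality estimator cannot be run as written. Baseline score, age, site or antiviral use could each serve as the layers, and each could give a different hazard ratio or mortality difference. If the choice is made after the data are seen, it is open to question. The reported primary hazard ratio may also be stratified while the primary test is not.

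**Unused prognostic information.** The event is reaching score 5 or above, and patients start at different distances from it. If the score predicts recovery and the relative benefit is similar at each score, a log-rank that pools the scores has less power than one that compares the arms within score. The data needed are already collected.

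**Working it through.** **Design figures (section 10.1).** The plan assumes that "the improvement hazard ratio (HR) was 1.54", with a control median of 11 days, while "the median time to improvement in the treatment group is projected as 7.14 days". It uses one-sided 0.025 and 208 events for 80% power. It adds: "Assuming 78% recovery rate, 270 participants will be enrolled in this trial".

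- 11/7.14 = 1.54; 208/0.78 = 267, close to 270; 0.7 × 208 = 145.6, so 146. These agree.
- Events for 80% power (Schoenfeld): 4(1.960 + 0.842)²/(ln 1.54)² = 31.4/0.1864 = 169, or 171 with the O'Brien-Fleming look. The stated 208 is not reproduced.
- Power at 208 events: Φ(√208 × 0.4318/2 − 1.960) = Φ(1.154) = 87.6%. This is why the table below starts near 88%. The mismatch with 80% is a separate matter.
- The two medians alone imply 1 − 2^(−28/11) = 82.9% and 1 − 2^(−28/7.14) = 93.4% recovered by Day 28, on average 88.1%. To match the plan's 78%, the medians were scaled up.

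**Tests compared.** Plain: Z = (O − E)/√V over all patients. Stratified: Z = Σ(Oₖ − Eₖ)/√ΣVₖ over scores k = 2, 3, 4.

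**Assumptions.** The score mix and recovery by score are not in the documents. The simulation used N = 270 at 1:1, exponential times rounded up to whole days, follow-up to Day 28, one-sided 0.025 and a hazard ratio of 1.54 in each score. The gradient is the control median in score 2 divided by that in score 4, with score 3 at the geometric mean. There were 20,000 trials per case (standard error at most 0.35 point).

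Power %, plain / stratified, by mix of scores 2/3/4:

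| Gradient | 15/35/50 | 10/20/70 | 5/25/70 |
|---|---|---|---|
| 1 (not prognostic) | 87.9 / 87.5 | 87.5 / 87.0 | 87.9 / 87.5 |
| 2 | 85.4 / 87.0 | 86.2 / 87.9 | 86.3 / 87.2 |
| 3 | 82.1 / 87.6 | 83.1 / 87.2 | 84.1 / 87.1 |
| 4 | 78.0 / 87.5 | 80.4 / 87.5 | not run |
| 5 | 74.7 / 87.6 | 78.5 / 87.5 | 80.6 / 87.7 |

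Type I error over 40,000 runs was 2.5 / 2.5, 2.5 / 2.4 and 2.6 / 2.7% at gradients 1, 3 and 5.

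**Variations.**

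- Keeping the 11-day overall control median and reaching 78% through random loss to follow-up (first two mixes): gains of 2.1/2.0, 6.2/5.4 and 13.7/10.9 points at gradients 2, 3 and 5.
- Reading 1.54 as the overall hazard ratio, so that the within-score ratio is 1.56 to 1.67: plain power stays at 87 to 88%, and the gains are 1.6/1.5, 4.4/3.6 and 7.9/6.7.
- More patients in score 2 (mix 30/35/35): plain power is 78.3% against 86.9% stratified at about 3.3-fold, and about 77 to 78% plain at 3.5-fold.

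Unequal hazard ratios, stratified minus plain in points (15/35/50, then 10/20/70):

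| HR in scores 2/3/4 | Gradient 2 | Gradient 3 | Gradient 5 |
|---|---|---|---|
| 2.0/1.7/1.3 | −2.2, −3.2 | −1.2, −1.6 | +1.8, +1.4 |
| 1.8/1.6/1.4 | −0.6, −0.9 | +1.3, +1.5 | +6.7, +5.6 |
| 2.2/2.2/1.0 | −2.0, −3.5 | −5.7, −6.5 | −9.2, −8.8 |
| 1.3/1.5/1.7 | +4.6, +2.9 | +9.2, +5.3 | +17.7, +10.5 |

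**Deaths.** Section 10.4.1 censors deaths on D29, so they stay at risk until then. The figures above leave this out. With a control median of 11 days and 10.7% mortality in every score, a non-prognostic score gives 66.0 / 65.8%. Assumed mortality of 30/12/4% by score has the same total at mix 15/35/50: 0.15 × 30 + 0.35 × 12 + 0.50 × 4 = 10.7%. At gradient 2, two runs (8,000 and 4,000 trials) then give 64.5 / 73.0% and 65.9 / 74.1%, a gain of about 8 points.

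**The case against.** The plain log-rank is valid and its form is fixed. The undefined layers therefore affect the reported hazard ratios and the mortality estimate, not the primary decision. That stands: a reader might infer that the primary result could be steered by choosing strata, and the documents do not support it.

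A reader might also infer that the plan disregards the baseline score. It does not. Sensitivity analysis (1) examines it, and the separate statistical analysis plan may name it as a stratum.

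The strongest objection is that the gain is not established. The documents give no score mix, no medians by score and no effect by score, and stratifying loses power if benefit is concentrated in the sicker patients. This limits the size and certainty of the claim. It does not remove it, because section 10.1 plans on a single hazard ratio and gives no reason to expect benefit mainly in scores 2 and 3.

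Finally, a stratified p-value compares arms within score, while the Kaplan-Meier curves, medians and cumulative rates in section 10.4.1 are marginal. That is a real cost in presentation.

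**Conclusion.** The concern holds as a recommended improvement, with moderate confidence. The primary test is valid but may give up power, and three other analyses lack named strata in the available text.

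With a hazard ratio of 1.54 within each score, 78% events and 15% or fewer patients in score 2, the gain is about 1 to 2 points at a twofold gradient, 3 to 6 at threefold and 7 to 14 at fivefold. If 1.54 is the overall hazard ratio, the gains are about 1.5, 4 and 7 to 8 points. With the death rule, absolute power is lower for both tests, and the gain is larger if mortality differs by score.

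The downside is under 1 point if the score is not prognostic, about 2 to 3 points if benefit is moderately larger in sicker patients and the gradient is weak, and up to about 9 points if benefit is confined to scores 2 and 3.

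Two stronger readings fail. It does not follow that the plain test misses 80% power: with a common hazard ratio and the death rule left out, that needs a steep gradient, and how steep depends on the mix (about fourfold with 15% in score 2, about 3.3-fold with 30%). Nor is the death rule independent of stratification: that appears so only when mortality is the same in every score.

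**What to change.** Before the unblinded look at 146 events:

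1. In section 10.4.1, make the primary test a log-rank stratified by the baseline NIAID score (2, 3, 4) recorded at screening, and restate the hypotheses as comparisons within score.
2. Name the same strata for the Cox models in sections 10.4.1 and 10.4.2 and for the Mantel-Haenszel mortality estimator.
3. Compute the section 10.5 conditional power from the same stratified statistic.
4. Keep the unstratified log-rank as a sensitivity analysis, beside the marginal Kaplan-Meier summaries, and say in the report that the p-value and the curves answer slightly different questions.

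If the sponsor expects benefit mainly in scores 2 and 3, keep the plain test as primary and do step 2 only. If the separate statistical analysis plan already names strata, step 2 reduces to a cross-reference.

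The cost is a short amendment to three sections, with no new data, visits or patients, plus the possible power losses given in the verdict.
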